**Figure 2. Study Timeline**

## 6. SELECTION & RECRUITMENT OF PARTICIPANTS

### **Study Population**

The study population will consist of 72 AYAs with SCD recruited from the CCHMC Sickle Cell Clinic. Eight (8) participants will be recruited for Aim 1 (feasibility, acceptability, intervention refinement) and 64 participants for Aim 2 (pilot two-arm randomized trial comparing efficacy of *SCThrive* to Attention Control) with the goal of retaining 54 for analyses (see recruitment strategies).

### **Inclusion Criteria**

We will use the following inclusion criteria for study participants:

- 1) Patient of CCHMC Sickle Cell Clinic.
- 2) Confirmed diagnosis of SCD with SS, SBThal or SC genotype.
- 3) 13-21 years of age.
- 4) On or eligible for disease-modifying therapies.
- 5) Caregiver (or AYA  $\geq$  18 years) consent that the participant will be the sole user of the tablet, report immediately if it is damaged or lost, return it at the end of the study, and log on to sessions from a private location.

### **Exclusion Criteria**

We will use the following exclusion criteria for study participants:

- 1) another chronic disease (which would complicate measurement of behavioral activation);
- 2) Non-English-speaking (<5% of the target population); or
- 3) cognitive or psychiatric disorder that the physician or study therapists believe would impair study participation. Patients who desire participation but are not eligible will be referred to the SCD Clinic social worker for assistance with self-management as this is the usual procedure.

### **Recruitment**

Potentially eligible AYAs will be identified through CCHMC's electronic medical record (EMR). Those meeting entry criteria will be sent a letter and flyer signed by the PI and the hematology clinical director telling them about the study and offering them the opportunity to call if interested. A trained clinical research coordinator will follow-up with a phone call to eligible participants to describe the study, answer any questions and schedule a time for interested participants to come in for a baseline visit. Eligible participants with a scheduled clinic visit will be approached to see if they would like to enroll during the visit. Eligible patients who are hospitalized will be approached only if the medical team feels it is appropriate or the patient requests more information about the study. After written informed consent/assent is obtained, AYAs and caregivers will complete baseline measures.

We will screen 85-100 AYAs with SCD (eligible pool) with the goal of recruiting 64 new AYAs with SCD (did not participate in Aim 1) using Aim 1 inclusion/exclusion criteria. After baseline assessment, we will review EMR data to determine disease severity (severe = history of acute chest syndrome, prior stroke or more than three vaso-occlusive crises in the past three years; not severe = these complications are not present).

The study statistician will use computer-generated randomization tables. Participants will be blocked on age (ages 13-17; ages 18-21) and disease severity (severe/not severe) and then randomized to one of the study arms to ensure equal distribution across groups.

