## 3. BACKGROUND

Adolescents and young adults (AYAs) with SCD have poor health outcomes. SCD is the most common genetic disorder in the U.S. affecting approximately 100,000 individuals, the majority of whom are African-American (approximately 1 in 400 African-American births). SCD is first identified during infancy, but the AYA years are a particularly vulnerable time when complications (e.g. chronic pain due to organ or bone damage, pulmonary hypertension, renal and cardiac dysfunction, or stroke) increase. SCD pain is severe, unpredictable, and recurrent, and accounts for the majority of Emergency Room (ER) visits and hospitalizations. AYAs with SCD have more ER visits than other age groups of SCD patients (3.61 per patient per year vs. 2.59 per patient per year). SCD accounts for approximately 100,000 hospitalizations per year (estimated \$488 million in healthcare costs). AYAs with SCD have higher 30 day and 14 day re-hospitalization rates than other SCD patients (41.1% and 28.4% respectively). Mortality rates for AYAs are also high, ranging from 6-20 percent. Approximately, 11% of AYAs with the most severe genotype (Hb SS) are at risk for over strokes. Silent strokes are frequent in all genotypes (37% of patients age 14 or older). Regrettably, the risk of stroke increases into adulthood and 50% of adults with SCD with no documented history of stroke have neurocognitive limitations. Furthermore, empirical studies confirm that AYAs with SCD are at risk for depression and anxiety, impairments in quality of life, and delays in social functioning.

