#### 4. STUDY DESIGN

**Aim 1:** We will conduct a mixed-methods study (quantitative and qualitative). Eight AYA with SCD ages 13-21 will participate in the *SCThrive* six-week, mixed format (in-person and online) intervention. Participants will complete measures at baseline and post-intervention to assess feasibility and acceptability of data collection and management procedures. We will also obtain qualitative feedback (via focus groups) from participants about *SCThrive* content, format, feasibility and acceptability. Data will be used to refine and finalize the intervention protocol.

**Aim 2:** We will conduct a pilot 2-arm randomized controlled trial to test the initial efficacy of *SCThrive* in improving BA relative to an Attention Control in AYAS with SCD ages 13-21. AYA with SCD will first be dichotomized by age (13-17 and 18-21) and disease severity (severe/non-severe). Participants will be categorized as severe if they have a history of acute chest syndrome, prior stroke or more than three hospitalizations for vaso-occlusive crises in the prior 3 years. Participants will be categorized as not severe if these complications are not present. Participants within each of the 2 (age; 13-17 years or 18-21 years) by 2 (disease severity; severe or not severe) cells will be randomized into the *SCThrive* intervention arm or an attention control arm (e.g., stratifying participants based on age and disease severity prior to random assignment).

Study participation includes a baseline assessment, after which participants will be randomized to the *SCThrive* intervention arm or attention control arm. This is followed by 6 weeks of intervention (*SCThrive*) and post-treatment assessment. Given the grant timeline, only a subset of participants will be followed in the post-treatment period. Fourteen *SCThrive* intervention arm participants will complete an online/in-person booster session at 6 weeks post-treatment and 14 attention control participants (N=14) will receive a follow-up phone call at 6 weeks post-treatment. These participants will also complete a follow-up assessment 6 weeks after treatment ends.

Our **primary outcome** will be for participants in the *SCThrive* group to demonstrate greater BA at post-treatment than the attention control group. Our **secondary outcome and exploratory aim** will be greater improvements in self-management behaviors and quality of life at the six-week follow-up.

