**Power Analysis:** We chose the PAM-13 (BA) as our primary outcome for power estimates because the General Linear Modeling analyses found a significant improvement in PAM-13 means from pre-test to post-test for the in-person self-management versus the self-management online portal groups, whereas the responsiveness of the other measures (e.g. SCD quality of life) may require a longer time-frame. The average effect size (eta-squared) for the change in BA was  $\eta^2 = 0.14$ , which is a large effect. A 2 (treatment vs. control) by 2 (pre-test, post-test) mixed effects ANCOVA power analysis was conducted using the internal Monte Carlo simulation capabilities of Mplus (Version 1.20) under the following assumptions: 1) the attention control arm will show a  $d = 0.30$  effect size improvement in BA from pre-test to post-test, 2) based on the effect size obtained from pilot data analyses (i.e.,  $\eta^2 = 0.14$ ), the *SCThrive* intervention arm will show a  $d = 0.90$  effect size improvement from pre-test to post-test, 3) participants assigned to the *SCThrive* intervention arm will show an incremental effect of  $(0.90 - 0.30 = 0.60)$   $d = 0.60$  over participants assigned to the attention control arm, and 4) the inclusion of two control covariates (treatment type and baseline healthcare utilization), together with blocking on participant age and disease severity prior to randomization, will explain 40% (i.e.,  $R^2 = 0.40$ ) of post-test BA score variance. Results from the Monte Carlo simulation analyses based on 5,000 simulated datasets showed power will be  $> 0.80$  to detect the  $d = 0.60$  anticipated incremental improvement for the *SCThrive* intervention arm if recruitment,  $N = 64$ , results in a post-attrition  $N = 54$  ( $N = 27$  per group) available for statistical analysis.

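### The severity stratum used in randomisation is defined by admissions for crises in Study Design and by crises in Recruitment, so some patients have two possible strata

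*Combined protocol and SAP*

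**What the plan says.** Section 4 (Study Design, Aim 2) splits participants by age (13-17, 18-21) and by severity, and randomises within the four cells, described as "stratifying participants based on age and disease severity prior to random assignment". A participant is severe with a history of acute chest syndrome, a prior stroke, or "more than three hospitalizations for vaso-occlusive crises in the prior 3 years".

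Section 6 (Recruitment) describes the same step as a procedure: "After baseline assessment, we will review EMR data to determine disease severity". The first two criteria are repeated, but the third is "more than three vaso-occlusive crises in the past three years", with no mention of admission. The section continues: "Participants will be blocked on age (ages 13-17; ages 18-21) and disease severity (severe/not severe) and then randomized".

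Section 9 (Power Analysis) relies on the factor. Two covariates (treatment type and baseline healthcare utilization), "together with blocking on participant age and disease severity prior to randomization, will explain 40" percent of post-test BA variance. The Aim 2 analysis in the same section specifies a mixed ANCOVA with group, time and their interaction. It does not list the strata as model terms.

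**The concern.** Both definitions are current text and both are stated as the operative rule. Neither defers to the other, and no section says what counts as a crisis. They are different counts from the medical record, so the rule chosen decides which randomisation list some participants enter.

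The Recruitment wording cannot safely be read as shorthand for admissions, because the protocol treats emergency visits and hospitalizations as separate events. Section 3 (Background) says that pain "accounts for the majority of Emergency Room (ER) visits and hospitalizations", and section 8 (Assessment Strategy) and Table 3 collect the two separately from the medical record. A reviewer following Recruitment could reasonably count a crisis treated in the emergency room without admission; one following Study Design could not.

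At stake are whether two people would assign the same stratum to the same patient, whether severity is balanced between arms as intended, and whether blocking delivers the precision that the power calculation credits to it.

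**Working it through.** **1. The two rules side by side.** Acute chest syndrome and stroke appear in both, so a patient with either is severe both ways. Only the third criterion differs. Take a patient with neither complication, five crises and one admission for crisis in three years:

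- Study Design: 1 admission does not exceed 3, so not severe.
- Recruitment: 5 crises exceed 3, so severe.

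Disagreement runs almost entirely this way. The reverse would need several admissions for one crisis.

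**2. The plan's own power figure.** Inputs from section 9: d = 0.60, R² = 0.40, 27 per group. Two-sided alpha of 0.05 is assumed, as section 9 does not state it.

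- Standardised effect after adjustment: 0.60/√(1 − 0.40) = 0.775.
- Noncentrality: 0.775 × √(27/2) = 2.846.
- Power: 0.812 by the normal approximation; 0.796 by noncentral t with 48 df (54 − 2 groups − 4 terms for the two covariates, age and severity).
- Recruitment: 54/0.85 = 63.5, so 64, as stated.

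The stated power of just over 0.80 is reproduced to within about a point, and there is no slack.

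**3. Cost of modelling the strata.** With the noncentrality unchanged, power is 0.797 at 50 df (no stratum terms) and 0.796 at 48 df (both terms). The lost degrees of freedom cost about 0.001.

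**4. How many patients could change stratum (illustration only).** The documents give no crisis rate and no admitted share. Their only event rate is the background emergency-visit rate, "3.61 per patient per year vs. 2.59 per patient per year", the first figure being for adolescents and young adults: 3.61 × 3 = 10.83 in three years. Assume that every such visit is a crisis, that 25% to 75% of crises lead to admission, and that 0% to 50% of patients are already severe through chest syndrome or stroke. Then

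number changing = 64 × (1 − share already severe) × [P(crises > 3) − P(admissions > 3)].

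| Count model | 25% admitted, 0% already severe | 75% admitted, 50% already severe |
|---|---|---|
| Poisson | 64 × (0.994 − 0.288) ≈ 45 | 64 × 0.5 × (0.994 − 0.961) ≈ 1 |
| Negative binomial, k = 1 | 64 × (0.702 − 0.284) ≈ 27 | 64 × 0.5 × (0.702 − 0.628) ≈ 2 |

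At an assumed 2 crises a year the ranges are about 6 to 50 (Poisson) and 3 to 26 (k = 1). The number is therefore not determined by the documents.

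**5. Does the broader wording empty the not-severe stratum?** Share with more than three crises in three years, before the other two criteria:

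- All 3.61 visits a year are crises: 0.994 (Poisson); 0.56, 0.70, 0.82 (negative binomial, k = 0.5, 1, 2).
- Half are: 0.79 (Poisson); 0.51 (k = 1).

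A two-level factor's capacity to explain variance scales with p(1 − p), at most 0.25. At p = 0.56 it is 0.246 and at p = 0.82 it is 0.148, or 98% and 59% of the maximum. Only the Poisson case with every visit counted (0.994 × 0.006 ≈ 0.006) makes the factor nearly useless.

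**The case against.** The strongest reply is that this is a wording slip in a single-site pilot with one record-review step, and that the treatment comparison is unharmed. The second part is right: whichever stratum is assigned before randomisation, allocation within it is random, so no bias follows. It is also true that the shared chest syndrome and stroke criteria limit the disagreement. If the medical record misses crises managed at home, the Recruitment count moves closer to the admission count. None of this tells the person doing the review which events to count.

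Three stronger conclusions that a reader might infer are not supported.

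- *That nearly everyone is severe under the Recruitment wording, so the factor separates no one.* This needs a background emergency-visit rate to be read as a crisis rate, with little variation between patients. Section 3 attributes only a majority of such visits to pain. With overdispersed counts a usable not-severe group remains. Nor is the admission wording shown to separate better: at an assumed 0.5 to 1.5 admissions a year, 7% to 66% (Poisson) exceed three.
- *That power falls to 0.73 or 0.68.* Those are the t-based values at R² = 0.30 and 0.20. Section 9 credits the 0.40 jointly to two covariates and to blocking on two factors, with no split. For severity alone to supply 0.10 to 0.20, even with a 50:50 split, the severe and not-severe groups would have to differ by √(0.10/0.25) = 0.63 to √(0.20/0.25) = 0.89 total SD on the PAM-13. That exceeds the treatment effect of 0.60. Baseline healthcare utilization is already a covariate and overlaps with either count. The two values illustrate an assumed loss and do not estimate it.
- *That only the admission count can be taken from the record.* Section 8 and Table 3 also take emergency visits from it, so ascertainability does not settle the choice.

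**Conclusion.** The inconsistency is real and follows from the text alone. Patients without chest syndrome or stroke whose crises did not all lead to admission can fall in different randomisation strata according to the section followed. The arm comparison stays valid. What is exposed is reproducible stratum assignment, balance on severity in a 64-person trial, and some part of the R² of 0.40. The size of that part cannot be stated, because the documents do not apportion it. It matters because planned power is about 0.80 with nothing in reserve. The count of affected patients likewise depends on assumed crisis and admission rates. The point merits correction before randomisation; it is not a threat to the trial's validity.

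**What to change.** Before randomisation, reconcile sections 4 and 6 to one severity definition in identical words. It should name the event in the medical record that counts towards the threshold and run the three-year look-back from the baseline date. Which definition to adopt is for the investigators; this review takes no position.

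In section 9, add the age and severity strata, as randomised, to the primary PAM-13 model, so that the analysis includes the blocking that the power calculation already credits.

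The cost is one sentence in each of the two definitions, one line in the analysis plan and a few degrees of freedom, about 0.001 in power. No procedures or participants are added.

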### **Retention**

To promote retention, AYAs will provide emails, all phone numbers, and contact information for others (i.e. parent-guardian, grandparents) in case they cannot be reached. In addition, participants will receive a calendar of study visits and electronic appointments. To facilitate communication, study staff will use a dedicated texting enabled cell phone.

## **7. PROCESS OF OBTAINING CONSENT**

Written informed consent/assent will be obtained by trained research staff when this is not possible phone consent will be obtained and written consent faxed or mailed to the CRC. All pertinent aspects of consent/assent will be covered including study purpose, risks/benefits, confidentiality, and right to withdraw. Patients will be informed that their care at CCHMC will not be affected by whether they choose to participate in the study. Caregivers and/or patients and study staff (co-investigators or research assistants) will sign and date the consent and permission form to document the informed consent process. Caregivers and/or patients will receive a copy of the signed and dated consent form to keep. Patients under age 18 will be asked to sign an assent form that is written at the 7th grade reading level or below.

## 8. STUDY PROCEDURES

**Aim 1:** We will conduct two successive groups of 4 AYAs with protocol refinements after the first group and further refinements after completion of the second group. These AYAs will participate in focus groups at the end of treatment to provide additional information about *SCThrive*'s format, content and acceptability. Participants will also complete measures at baseline and post-treatment (see Table 3).

All *SCThrive* participants will receive a Wi-Fi enabled, insured, tablet computer with a cellular data plan that will facilitate: 1) standardization of intervention delivery; 2) consistent access to a computer and internet service; and 3) study personnel monitoring of tablet use. During the first session, AYAs will be assigned a unique username and password for the *iManage* tool and sign a iPad use agreement (see epas). The CRC will provide instructions, demonstrate system features, and assist AYAs in starting their patient profile, selecting a self-management goal (action plan), and scheduling reminders. The CRC will be available by cell phone for troubleshooting.

After obtaining consent, a member of the research team will schedule the first study visit with the participants. Subsequent study visits will be scheduled via phone, e-mail, or in-person contact with a member of the research team. All study visits will last approximately one to two hours and will be conducted in a conference room in the D building, Behavioral Medicine and Clinical Psychology clinic space or online.

**Aim 2:** Participants will complete two or three study visits as part of this study. Study visits will occur at baseline (screening), post-intervention, 2 weeks post-intervention (week 8), and 4 weeks- post-intervention (week 12). The SCD population has a high rate of no-shows and cancellations due to psychosocial factors that interfere with access to treatment but to increase the likelihood of participant retention while minimizing participant burden, measures can be completed within a one month window of each study visit date. To minimize participant burden, follow-up study visits will be coordinated with SCD clinic appointments when possible or scheduled at another time convenient for the participant and their family. To maximize attendance at study visits, a member of the research team will remind the participants of upcoming research visits via phone call, text, or e-mail as preferred by the participant.

*SCThrive arm.* Four successive groups with four to eight participants per group will be conducted. Participants will receive the finalized six-week *SCThrive* intervention using procedures described in Aim 1. To encourage retention and skill maintenance, participants will receive one online/in-person booster session two weeks after treatment ends. Based on feedback from the Intervention Development Team we will allow participants who cannot attend the in-person session due to illness or other factors to attend online via ZOOM. We will also allow participants to review a missed session recording before the next session with the CRC.

*Attention control arm.* Additional trained therapists (not conducting *SCThrive*) will conduct the attention control intervention which consists of six weekly 15-20 minute individual phone calls via Zoom. Participants will receive one online booster session two weeks after treatment ends.

*Assessment Strategy.* AYAs will complete questionnaires assessing BA, self-management behaviors (including healthy lifestyle behaviors), quality of life, and depressive symptoms (which can impact BA; Beck Depression Inventory-II), at baseline, post-treatment, and six-weeks after treatment (see Table 3). Caregivers or AYAs  $\geq$  age 18 will complete demographic (e.g. parental

education, family income), psychosocial (Psychosocial Assessment Tool – PAT 2.0 General), barriers to care (Barriers to Care Questionnaire – BCQ) measures at baseline. Caregivers will also complete a quality of life measure at baseline and post-treatment. We will collect ER visits, disease severity, and hospitalization data from the EMR. *SCThrive* satisfaction and usefulness will be assessed after each session. Feasibility, acceptability, and *iManage* usage measures will be completed at post-treatment. The *iManage* tool will provide usage data on the number and frequency of logins, pages visited, time spent on each page, and number and time of action plan reminders. Based on feedback from the pilot group, we added a health motivation measure (Treatment Self-Regulation Questionnaire – TSRQ) to capture the social support and healthcare knowledge and skills participants reported were significant benefits of participating in the intervention. In addition, since our original submission an SCD-specific measure of self-management/ transition readiness has been published. We have now added these two measures to the battery and will increase our compensation accordingly. We also added a feasibility measure for the SHealthEd treatment and a qualitative interview for the SCThrive treatment to help us better understand participant perceptions and experiences with the intervention.

